### 6.5.3. Change from Baseline

Change from baseline is calculated as

(post-baseline result – baseline result).

If either the baseline or the post-baseline result is missing, the change from baseline and percentage change from baseline are both set to missing.

### 6.5.4. Visit Windows

Except for the Randomization Visit, which is designated as Study Day 1, all originally planned visits given in the protocol schedule of assessments from the Screening visit (Visit 1A) through the End of Study visit (Visit 12: Week 48) have a specified visit window. The table below gives the window for each of these visits.

During the first screening episode, subjects may be re-tested for specific inclusion and exclusion criteria that were not met at the initial testing. The re-test must take place within 10 days of the original screening date. Subjects who do not meet all the eligibility criteria within 21 days of the screening visit are considered screen failures.

Depending on the reason for screen failure, subjects may be re-screened for study entry at least 2 weeks after their original screen failure date. Subjects who are to be re-screened must give informed consent again no more than 7 days prior to rescreening.

**Table 2: Visit Windows (Study Days)**

Visit Number: Visit Name	Analysis Visit Name	Relative Target Day (Study Day)	Visit Window (Study Day Interval)
Visit 1A: Screening a	Screening	-14	<1
Visit 1A: Retest a	Screening	-9 a	<1
Visit 1B: Rescreen b	Screening	-14 b	<1
Visit 1B: Retest b	Screening	-9 b	<1
Visit 2: Randomization	Baseline	1	1
Visit 3: Week 2	Week 2	15	[2, 22]
Visit 4: Week 4	Week 4	29	[23, 43]
Visit 5: Week 8	Week 8	57	[44, 71]
Visit 6: Week 12	Week 12	85	[72, 99]

Document: \\quintiles.net\enterprise\apps\sasdata\sasb\sas\Keryx\KRX-0502\Biostatistics\Documentation\SAP\

Visit Number: Visit Name	Analysis Visit Name	Relative Target Day (Study Day)	Visit Window (Study Day Interval)
Visit 7: Week 16	Week 16	113	[100, 127]
Visit 8: Week 20	Week 20	141	[128, 155]
Visit 9: Week 24	Week 24	169	[156, 197]
Visit 10: Week 32	Week 32	225	[198, 253]
Visit 11: Week 40	Week 40	281	[254, 309]
Visit 12: Week 48	Week 48	337	>309
Visit Early Termination: Early Termination (ET) c	Early Termination		

a Any retest for specific inclusion and exclusion criteria that were not met at the initial testing may occur within 10 days of the original screening date. Therefore, the visit window, including start and end dates, for the retest is the same visit window as that for the original screening visit. A subject can have only 1 retest based on the original screening results.

b Visit window for the rescreen visit has a study day interval relative to Day 1, equivalent to that for the original screening visit but because rescreening of a subject must be at least 14 days after the subject's original screen failure date the actual start and end dates on a subject's Screening Visit window and the Re-Screening Visit window differ. A subject can have only 1 retest based on the re-screening results. Any retest for specific inclusion and exclusion criteria that were not met at re-screening may occur within 10 days of the re-screening date.

c Early Termination visits may fall within a visit window corresponding to a planned study visit. If this is the case, the ET visit will be labeled and summarized with the analysis visit name corresponding to the visit window.

Multiple assessments may occur within the same window for a variety of reasons, for example, assessments to determine if the study drug dose should be adjusted. While there is only one planned scheduled dose adjustment, unscheduled dose adjustments for a subject may be necessary at any time during the study.

The protocol includes guidance on making dosing adjustments which are dependent on specific central laboratory results. Laboratory values will be checked at each scheduled visit and the study drug dose may be adjusted in response to these results. When laboratory retesting is necessary, it will be done as an unscheduled visit, unless it coincides with a scheduled visit.

Given the time lag in obtaining lab results and communicating the desired dose adjustment to the subject via telephone the time that the new prescription is to start and the subsequent follow-up blood draws for testing may or may not be in a single window for an originally planned visit given in the protocol's schedule of assessments. There may be multiple assessments falling in the same window and multiple assessments related to a single event may be taken during the window for more than one scheduled visit.

Additionally, when a subject discontinues from the study, the assessments made at the Early Termination visit may fall within a window for one of the originally planned visits given in the protocol's schedule of assessments.

When multiple assessments occur within the same window, the one whose date of assessment is the largest study day in the window will be considered as the observed assessment value for that scheduled visit study day.

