All dose changes should be based on Central Laboratory values. Laboratory results will be checked at each scheduled visit, and the dose may be adjusted in response to these results. When repeat testing of laboratory values is necessary, it will be done as an unscheduled visit, unless it coincides with a scheduled visit. Repeat laboratory testing to guide KRX-0502 dosing should include a CBC, iron studies, and CCP. The Investigator should contact the subject as soon as possible after review of the laboratory results for any scheduled or unscheduled dose adjustments.

Additional information regarding drug-drug interactions is provided in [Section 14](#).

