7.5.2. Unscheduled Dose Adjustments

Unscheduled dose adjustments may be necessary at any point during the study. Below guidance and the dosing algorithms depicted in [Figure 2](#), [Figure 3](#), and [Figure 4](#) aim to assist the Investigator with decision making about dose modification in the presence of laboratory abnormalities or AEs. They are not intended to define a standard of care, nor should they be interpreted as prescribing an exclusive course of management. Investigators are responsible for evaluating the appropriateness of applying these guidelines to any particular clinical situation for an individual subject. Dose interruption refers to holding of the drug, usually for a short term with the intent to resume dosing when possible. To discuss dosing decisions, including extended dose interruption, Investigators should contact the Medical Monitor.

- Serum phosphorus <2.5 mg/dL:
 - If serum phosphorus is <2.0 mg/dL, interrupt dosing.
 - Two weeks after interrupting the dose, repeat the laboratory tests:
 - If serum phosphorus is ≥ 2.5 mg/dL, resume dosing at the dose prior to the dose interruption.
 - If serum phosphorus is ≥ 2.0 to <2.5 mg/dL, resume dosing at a reduced dose compared to the dose prior to the dose interruption.
 - If serum phosphorus is <2.0 , continue dose interruption.
- If serum phosphorus is ≥ 2.0 to <2.5 mg/dL, reduce the KRX-0502 dose by 1 to 3 tablets/day without complete dose interruption.
 - Two weeks after reducing the dose, repeat the laboratory tests:
 - If serum phosphorus is ≥ 2.5 mg/dL, increase the dose to the dose prior to the dose reduction.

- If serum phosphorus is ≥ 2.0 to < 2.5 mg/dL, reduce the dose again.
- If serum phosphorus is < 2.0 mg/dL, interrupt dosing.
- Decisions about resuming or increasing dosing and at which dose should take into consideration the absolute levels and trends of the serum phosphorus in the context of the prior dose changes as well as Hgb and TSAT.
- After resolution of a low serum phosphorus, an attempt should be made to increase the dose to the highest dose tolerated prior to the dose interruption or reduction, if supported by the Investigator's clinical judgement.

TSAT $\geq 50\%$:

- If TSAT is $\geq 50\%$, repeat laboratory tests with care to assure that the blood draw is performed before dosing with KRX-0502.
 - If the repeat TSAT is $\geq 70\%$, interrupt dosing.
 - If the repeat TSAT is ≥ 50 and $< 70\%$, the response should consider the Hgb level.

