 - If Hgb is ≥ 12 g/dL, interrupt dosing.
 - If Hgb is < 12 g/dL, reduce the dose.
 - If the repeat TSAT is $< 50\%$, continue current dose and repeat laboratory tests at the next scheduled visit.
- After a dose reduction, repeat laboratory tests at the next scheduled visit.
- Two weeks after interrupting dosing, repeat laboratory tests.
 - If the repeat TSAT is $\geq 70\%$, continue dose interruption and repeat laboratory tests after 2 weeks.
 - If TSAT is $< 70\%$, consult the Medical Monitor.
- Decision about resuming and increasing dosing and at which dose should take into consideration the absolute levels and trends of the TSAT and Hgb in the context of the prior dose changes, as well as serum phosphorus levels.
- After resolution of an elevated TSAT, an attempt should be made to increase the dose to the highest dose tolerated prior to the dose interruption or reduction, if supported by the Investigator's clinical judgement.

[figure not shown]
Elevated ferritin:

An elevated ferritin level alone (ie, ferritin > 1000 ng/mL) does not require dose interruption or dose reduction because it is a poor indicator of iron stores in patients with CKD. However, an elevated ferritin level should prompt clinical evaluation for inflammation or infection and, in review together with the Hgb and TSAT, may lead an Investigator to the decision to interrupt or reduce dosing.

Other laboratory abnormalities or AEs:

If an unscheduled dose reduction or interruption is necessary due to another laboratory abnormality or AE, upon resolution of the laboratory abnormality or AE the dose should be resumed and/or subsequently increased to the highest dose tolerated prior to dose reduction or interruption, if supported by the Investigator's clinical judgement.

Figure 2: KRX-0502 Dosing Algorithm: Serum Phosphorus <2.0 mg/dL

[figure not shown]

Phos=serum phosphorus.

Note: All serum phosphorus values are presented in mg/dL.

Decisions about resuming or increasing dosing, and at which dose, should take into consideration the absolute levels and trends of the serum phosphorus in the context of the prior dose changes as well as Hgb and TSAT.

To discuss any dosing decisions, including extended dose interruption, Investigators should contact the Medical Monitor.

[figure not shown]
Figure 3: KRX-0502 Dosing Algorithm: Serum Phosphorus ≥ 2.0 to < 2.5 mg/dL

Phos=serum phosphorus.

Note: All serum phosphorus values are presented in mg/dL.

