#### 9.4. Routine Laboratory Data

Tables for three groups of laboratory parameters, hematology, clinical chemistry and urine chemistry will be provided. All laboratory tests will be listed. Laboratory test results for all subjects in the safety analysis set will be summarized using descriptive statistics. For the continuous laboratory parameters descriptive statistics will be displayed for the actual values and for the change in value from baseline to each scheduled post-baseline visit. Tables and listings for the 24-Week Analysis will only display statistics for visits during the Dose Titration period. Tables for the Final Analysis will show those visits during the Dose Maintenance period in addition to the Baseline visit but listings for the Final Analysis will be based on observations over the entire study.

Subject's laboratory results for the following laboratory parameters:

---

Document: \\quintiles.net\enterprise\apps\sasdata\sasb\sas\Keryx\KRX-0502\Biostatistics\Documentation\SAP\

- Ferritin
- TSAT
- Hemoglobin
- Serum Phosphorous

are of special interest. Their values will be classified as low or where relevant one of its sub-categories, normal, or high or where relevant one of its sub-categories given the range of values used to identify clinically meaningful abnormalities in a patient with CKD.

The thresholds for potentially significant abnormalities are based upon Common Terminology Criteria for Adverse Events v4.0 (CTCAE) grades and/or clinically meaningful abnormalities in a CKD stage 3- 4 patient. The thresholds are listed in Table 4 below. Table 4 also includes these categories for impaired liver function, i.e., the categories of total bilirubin, ALT and AST as related to identification of potential Hy's Law cases.

Shift tables, for the laboratory parameters of special interest will be produced showing the number and percentage of subjects with Baseline result in each of the categories, low or where relevant the sub-categories of low, normal and high or where relevant the sub-categories of high, whose result at the post-baseline visit is in each of these categories. The shift tables will be provided by starting dose group and the two treatment groups combined. A by subject listing by visit of the subject's values with their classification relative to potentially significant abnormality for each laboratory parameter of special interest will be provided.

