**Table 4: Clinical Laboratory Potentially Clinically Significant Criteria**

Parameter	Threshold (Low Criterion/ High Criterion)	Low Criterion (Subcategories)	High Criterion (Subcategories)
Iron Parameter (unit)			
Ferritin (ng/mL)	Clinical	NA	High 1: > 500 to 1000, High 2: > 1000
Transferrin saturation (%)	Clinical	NA	High 1: > =50 to <70 High 2: > =70
Hematology			
Hemoglobin (g/dL)	CTCAE grade 3 /Clinical	< 8.0	> 13
Chemistry			
Phosphorous (mg/dL)	CTCAE grade 2 /Clinical	Low 1: ≥2.0 to <2.5, Low 2: < 2.0	> 9.0
Liver Function			
Hy's Law (Impaired Liver Function)	CTCAE grade 2 /DILI*	NA	High 1: ALT or AST > 3 x ULN to 5 x ULN High 2: ALT or AST > 5 x ULN
Total serum bilirubin value	DILI*	NA	> 2xULN

\*DILI = Drug Induced Liver Injury

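### At Weeks 32 and 40 a two-week retest after a phosphorus-driven dose change can replace the triggering result, so the Final shift table may undercount low phosphorus

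*SAP*

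**What the plan says.** **Choice of value.** SAP 6.5.4 expects several results in one window, names dose-adjustment testing as a cause, and resolves it by date alone: "the one whose date of assessment is the largest study day in the window will be considered as the observed assessment value". Scheduled draws get no priority, and safety tables are not exempted. SAP Table 2 sets Week 32 at days 198 to 253 (target 225) and Week 40 at days 254 to 309 (target 281).

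**Retests.** For low phosphorus, Protocol 7.5.2 advises: "Two weeks after interrupting the dose, repeat the laboratory tests". It advises the same interval after a phosphorus-driven reduction. For TSAT of 50% or more, a repeat comes first and decides the action. If dosing is then interrupted, "Two weeks after interrupting dosing, repeat laboratory tests"; if the dose is only reduced, "After a dose reduction, repeat laboratory tests at the next scheduled visit". Protocol 10.6 carries these instructions into the Dose Maintenance Period. Protocol 7.5 adds: "Repeat laboratory testing to guide KRX-0502 dosing should include a CBC, iron studies, and CCP".

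**Safety summary.** SAP 9.4 builds shift tables for ferritin, TSAT, hemoglobin and phosphorus from the category of the result at the post-baseline visit. It describes no table of worst post-baseline category. For the Final analysis, "Tables for the Final Analysis will show those visits during the Dose Maintenance period in addition to the Baseline visit". The low phosphorus categories in SAP Table 4 are "Low 1: ≥2.0 to <2.5, Low 2: < 2.0", the same cut-points that prompt the dose changes in Protocol 7.5.2.

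**The concern.** The shift table uses the thresholds that set off a dose change, but the value it classifies may be the one drawn after that change, off drug or at a reduced dose. An illustration with invented values: phosphorus is 1.8 mg/dL at Week 32 on day 225, dosing is interrupted the same day, and the retest on day 239 reads 2.6 mg/dL. Day 239 is inside the window, so Week 32 is recorded as 2.6 and the Low 2 result is not counted.

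At stake is a small count in a planned safety summary. The replacement follows corrective action, so the error tends towards too few low-phosphorus results. Of the three post-baseline visits in the Final tables (Weeks 32, 40 and 48), the first two are exposed.

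**Working it through.** **1. Reproduce the windows.** Each upper bound is the midpoint between successive target days: (225 + 281)/2 = 253 for Week 32 and (281 + 337)/2 = 309 for Week 40. Both match SAP Table 2. Each bound lies 28 days past its target (253 − 225 and 309 − 281).

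**2. Place the retest.** Retest day = visit day + lag from draw to dose change + 14. The Protocol Table 2 tolerance is ±7 days, giving visits on days 218 to 232 and 274 to 288. The documents mention a lag but do not quantify it, so it is varied below.

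- Latest allowed Week 32 visit: 253 − 14 − 232 = 7 days of lag before the retest leaves the window.
- Latest allowed Week 40 visit: 309 − 14 − 288 = 7 days.
- The next scheduled visits (earliest days 274 and 330) lie outside these windows and cannot displace the retest.

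**3. Share of retests landing in the triggering visit's window.** All 15 allowed visit days and all whole-day lags are weighted equally. With v the visit's offset from target, the condition is v + lag ≤ 14.

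| Assumed lag | In window | Share |
|---|---|---|
| 0 to 7 days | 120 of 120 | 100% |
| 0 to 10 days | 159 of 165 | 96% |
| 0 to 14 days | 197 of 225 | 88% |
| TSAT route: two lags of 0 to 7 days (confirmatory repeat, then interruption) | 876 of 960 | 91% |

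These are shares of retests, not of subjects.

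**4. Effect on the table.** A retest in the same category changes nothing. A worse one is counted as worse. Only a milder one removes the triggering category.

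**5. Possible size, phosphorus only.** The documents give no trigger rate. Assumptions: 140 subjects at the visit (the plan's evaluable number), 1 to 5% with phosphorus below 2.5 mg/dL, guidance followed, overlap of 88 to 100%, and 50 to 100% of retests milder.

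- Low end: 140 × 0.01 × 0.876 × 0.5 = 0.6 subjects per visit.
- High end: 140 × 0.05 × 1 × 1 = 7 subjects per visit.
- With all 200 randomized subjects: 0.9 to 10.
- As a share of flagged subjects: 0.876 × 0.5 = 44%, up to 100%.

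**6. Effect on means.** If phosphate rises by an assumed 0.5 to 1.0 mg/dL on retest, the visit mean moves by 0.01 × 0.5 × 0.876 = 0.004 up to 0.05 × 1.0 × 1 = 0.05 mg/dL.

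**The case against.** The rule is deliberate. SAP 6.5.4 foresees follow-up draws sharing a window and gives one deterministic answer, which nothing else in the plan contradicts. Latest, scheduled-first and closest-to-target are all workable conventions. The abnormal values also stay visible: SAP 9.4 lists the special-interest parameters by subject and visit with their classification, lists every laboratory value, and Protocol 13.2.2 requires clinically significant values to be recorded as AEs. All of this stands. It limits the loss to a count in one summary table, but a listing does not supply that count.

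A reader might infer more than the documents support:

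- **That the overlap is certain.** It needs an in-tolerance visit, a retest on exactly day 14 and a lag of at most 7 days. A Week 32 visit on day 240 never overlaps (240 + 14 = 254). A day-232 visit with a 7-day lag and a day-15 retest also misses (254). Protocol 7.5.2 says of its guidance: "They are not intended to define a standard of care, nor should they be interpreted as prescribing an exclusive course of management".
- **That TSAT is affected in the same way.** There the confirmatory repeat, not the scheduled value, decides the dose change. A high scheduled TSAT may be a draw taken after dosing, and replacing it can improve the table. TSAT-driven reductions have no two-week retest. The subject counts above do not cover TSAT.
- **That every replacement hides harm.** Protocol 7.5.2 provides for a retest after a phosphorus-driven reduction that is unchanged or below 2.0 mg/dL.
- **That the Week 24 results are distorted.** The overlap exists there too (197 − 14 − 174 = 9 days of lag), but Final laboratory tables do not show Week 24. Whether later draws enter the 24-Week analysis depends on a laboratory cut that the SAP does not state. Its visit-date cut in section 9 names only AEs and exposure. This needs clarification; it is not a demonstrated fault.

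**Conclusion.** The point holds in a limited form. Where the protocol guidance is followed, the latest-in-window rule tends to understate low-phosphorus counts in the Final shift tables at Weeks 32 and 40 and, to a lesser extent, counts of confirmed high TSAT followed by interruption. The overlap is complete under the three conditions on visit day, retest day and lag, and 88% if lags spread over 0 to 14 days.

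Few subjects are likely to be affected. Protocol 5.2 reports that phosphate rarely fell below range in Study 306, this study uses a lower maximal dose (Protocol 6.2), and screening phosphate below 3.0 mg/dL is excluded. The range of 0.6 to 7 subjects per visit rests on assumed rates, not on figures in the documents.

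A reader might conclude that the visit rule must be rewritten for the efficacy models. The size of the effect on means does not support that. A new rule would also have to settle how Early Termination draws (Table 2, footnote c) and suspect draws are treated. This is a cheap improvement of minor severity.

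**What to change.** In SAP 9.4, add a shift table from baseline to worst post-baseline category, lowest and highest, for ferritin, TSAT, hemoglobin and phosphorus. Use all post-baseline central laboratory results, including unscheduled and Early Termination draws. For TSAT, where a confirmatory repeat was drawn before dosing, use the repeat in place of the value it was meant to confirm, or show the table both ways.

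Leave the visit-window rule for the efficacy models as it is. The cost is SAP wording, a way to identify TSAT confirmatory repeats and one extra safety table from data already collected. Its counts may look slightly less favourable than those in the by-visit tables.

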## **6.6. Handling of Missing Data**

### **6.6.1. Missing Efficacy Endpoints**

Subjects who discontinue will not be replaced. If efficacy endpoint data are missing, they will not be imputed.

Mixed models will be used to analyze the repeated measures data for visits up to and including Week 24 and Week 48. The Mixed Model Repeated Measures (MMRM) models described in section 8.2 implicitly adjust for missing data under the assumption of missing at random.

### **6.6.2. Missing Start and Stop Dates for Prior and Concomitant Medications and Medical Conditions**

Prior and concomitant medication missing start and stop dates will be imputed in accordance with the rules specified in section 7.5. Imputed dates will only be used to determine whether a medication is concomitant or not.

The rules for imputing medical history and medical conditions start and stop dates to identify those present at entry are equivalent to the rules given in section 7.5 for prior and concomitant medications, respectively.

### **6.6.3. Missing Start and Stop Dates for Adverse Events**

Missing stop dates for adverse events will not be imputed. Missing start dates for adverse events will be imputed in accordance with the rules specified in section 9.2.2. Imputed dates will only be used to determine whether an adverse event is treatment emergent or not.

### **6.6.4. Missing CKD Initial Diagnosis Date**

If the year part of the CKD diagnosis date is missing, it will not be imputed and CKD Initial Diagnosis Age (years) will be missing. If the year part of the CKD diagnosis date is not missing and either the month or day is missing, then the missing part of the date will be imputed as follows for the analysis:

- If the month is missing, then the month will be imputed as January.

- If the day is missing, then the day will be imputed as 01.

The imputed CKD diagnosis date will be concatenated with subject number and other subject characteristics on some of the by subject listings.

